5.8 Safety Data

The only safety information collected in this study is serious adverse events associated with the venipuncture that takes place on Day 1. All adverse events will be listed and, if there is a meaningful number of them, tabulated as well.

5.9 Handling of Missing and Incomplete Data

Subjects with missing data for baseline FcγRIIa will be excluded from all analyses. Missing values for other covariates will be imputed using a median value imputation for continuous variables and most frequent value imputation for categorical variables.

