#### 9.4.2 ANALYSIS OF THE PRIMARY OBJECTIVE

Cox proportional hazards models will be fit to compare the risk of the primary endpoint based on platelet expression of FcγRIIa as a continuous variable. Subjects will be followed until their earliest MI, stroke, or death. Patients who do not experience the composite endpoint will be censored at their last telephone follow-up. Time to the primary endpoint will be calculated as days from study enrollment. Models will be adjusted for potential confounders including sex and other subject demographics and medical history collected at baseline. In the pilot study, it was observed that older age, diabetes mellitus, and prior revascularization were associated with higher platelet FcγRIIa expression.

A set of sensitivity analyses will evaluate FcγRIIa as a binary endpoint, which each analysis using a different threshold for classifying FcγRIIa as high or low. In particular, these analyses will explore whether a binary or a continuous measure of FcγRIIa provides greater predictive value, and whether or not a threshold of  $\geq 11,000/\text{platelet}$  is optimal.

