5.7 Statistical Methods

5.7.1 Analysis of the Primary Objective

The primary analysis of the primary endpoint will be a Cox proportional hazards model. The dependent variable is the number of days from enrolment to the occurrence of a primary endpoint, with censoring at the last day of complete follow-up; independent variables will be FcγRIIa (measured in thousands), age in years, history of diabetes mellitus, prior revascularization, multi-vessel coronary artery disease (MVD) defined as ≥2 vessels or left main with a stenosis ≥50%, chronic kidney disease (CKD) defined as estimated glomerular filtration rate (GFR) < 60 ml/min/1.73 m², prior MI, hypertension, tobacco use, heart failure or LVEF<30%, previous stroke or transient ischemic attack, and peripheral arterial disease. Interest is in the FcγRIIa parameter: point estimate (increase in risk per 1000-unit increase in FcγRIIa), confidence interval and p-value. FcγRIIa will be declared to be associated with cardiovascular risk if the 2-sided p-value from this model is < 0.05.

A set of exploratory/sensitivity and subgroup analyses based on the Cox model will also be conducted.

- Instead of censoring at the last day of complete follow-up, censor at the last day of vital status follow-up
- FcγRIIa as the only covariate in the model
- Separate analyses of each component of the primary endpoint: MI and stroke, both censored at the last day of complete follow-up, and death, censored at the last day of vital status follow-up
- Run the primary model in subgroups defined by age (in decades), sex, history of diabetes and prior revascularization (including all covariates except the subgroup variable in the model)
- Run the primary model with the use of DAPT (any use prior to a primary endpoint), and its interaction with FcγRIIa, as additional covariates

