5.7.2 Analysis of the Secondary Objective

First Secondary Objective: Negative predictive value, positive predictive value, sensitivity, and specificity will be calculated. Prediction will be performed using a Cox regression model with the following predictors: platelet expression of Fc γ RIIa, sex, age, and clinical risk factors associated with increased cardiovascular risk. Evaluation of the model's error rates will be based on a leave-one-out cross-validation approach. Additional models will evaluate the performance of the predictive model using a continuous measure of Fc γ RIIa with the performance of predictive models using various binary measures of Fc γ RIIa.

Second Secondary Objective: The adjusted Cox proportional hazards model described for the primary objective analysis will be used to compare the bleeding risk as a function of Fc γ RIIa expression. One

model will include FcγRIIa as a continuous variable, and another using the dichotomized version of FcγRIIa selected as the optimal version for risk stratification.

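### SAP 5.9 fills missing covariates once with the median or most frequent value, which under-adjusts the FcγRIIa hazard ratio where confounders are incomplete; multiple imputation should be the primary method

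*SAP*

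**What the plan says.** SAP 5.9 treats the marker and the other covariates differently. For the marker, "Subjects with missing data for baseline FcγRIIa will be excluded from all analyses"; that rule is not at issue here. For everything else, missing values are to be "imputed using a median value imputation for continuous variables and most frequent value imputation for categorical variables", so each gap is filled once.

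The filled data feed the primary Cox model in SAP 5.7.1, which has FcγRIIa plus eleven adjustment covariates. Five of these (age, diabetes, multi-vessel disease, chronic kidney disease, prior MI) are also the risk factors in Protocol 5.1. The other six are prior revascularization and "hypertension, tobacco use, heart failure or LVEF<30%, previous stroke or transient ischemic attack, and peripheral arterial disease". The target of inference is explicit: "Interest is in the FcγRIIa parameter: point estimate (increase in risk per 1000-unit increase in FcγRIIa), confidence interval and p-value". So is the decision rule: "FcγRIIa will be declared to be associated with cardiovascular risk if the 2-sided p-value from this model is < 0.05". SAP 5.7.2 uses the same adjusted model for bleeding.

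Protocol 9.4.2 explains why adjustment is needed: in the pilot, "older age, diabetes mellitus, and prior revascularization were associated with higher platelet" FcγRIIa expression.

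Neither document gives an expected missing fraction, a mechanism, a variance correction for filled values, or a complete-case or multiple-imputation analysis. The sensitivity list in SAP 5.7.1 varies censoring, the covariate set, endpoint components, subgroups and DAPT use, but not the imputation rule.

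**The concern.** For a risk factor present in fewer than half of subjects, the most-frequent-value rule codes every missing entry as absent, whatever the subject's age, FcγRIIa or outcome. If a fraction m is missing completely at random, a fraction m of the true carriers is recorded as non-carriers. The model then adjusts for a diluted version of the confounder. Part of the confounder's effect stays in the FcγRIIa coefficient, and it adds to the apparent marker effect when the factor raises both FcγRIIa and risk.

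This bears on the headline result because the association is declared from that one coefficient. It also bears on bleeding: the study hypothesizes no association there, and leftover confounding could create one.

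**Working it through.** **Nothing to reproduce.** The plan gives no figure on missing data. Its power statement is not an input here.

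**Inputs from the documents.** 800 subjects and at least 80 events (SAP 5.10); two-sided 0.05 and the model above (SAP 5.7.1); the fill-in rule (SAP 5.9). With 10% missing on one covariate, 800 × 0.10 = 80 subjects would carry a filled value.

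**Assumed inputs.** Missing fractions, mechanisms, covariate prevalences and effect sizes are not in the documents.

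**Main simulation.** There were 800 subjects and about 87 events, with no true marker effect. The Cox model held FcγRIIa and eight covariates. Diabetes, prior revascularization, kidney disease and heart failure were incomplete together. Each scenario had 400 replicates. Multiple imputation used chained equations with 10 data sets; the imputation model included the event indicator and the Nelson-Aalen hazard. The shift is the mean log hazard ratio per SD of FcγRIIa under the SAP rule, minus that from the full-data fit.

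| Missing per covariate | Shift, SAP rule | exp(shift) | False positives, SAP rule | False positives, multiple imputation |
|---|---|---|---|---|
| 5%, at random | +0.016 | 1.016 | 4.8% | 5.0% |
| 10%, at random | +0.031 | 1.031 | 6.0% | 5.2% |
| 20%, at random | +0.059 | 1.061 | 7.5% | 5.0% |
| 30%, at random | +0.086 | 1.090 | 9.2% | 5.0% |
| 10%, depends on FcγRIIa and age | +0.106 | 1.112 | 15.8% | 6.0% |
| 20%, depends on FcγRIIa and age | +0.159 | 1.172 | 30.5% | 5.0% |
| 30%, depends on FcγRIIa and age | +0.192 | 1.212 | 38.5% | 5.0% |

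Here, at random means completely at random. Monte Carlo error near 5% is √(0.05 × 0.95 / 400) = 1.1 points. Full-data rates were 6.0% and 4.5% in the 20% and 30% random rows, and 7.0%, 6.8% and 4.3% in the last three. The shift under multiple imputation was at most +0.003.

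**Hand check.** With δ = shift / SE, the false-positive rate is about Φ(−1.96 + δ) + Φ(−1.96 − δ).
- 5% at random: δ = 0.016 / 0.123 = 0.13, giving 5.2%.
- 20% at random: δ = 0.059 / 0.120 = 0.49, giving 7.8%.
- 30%, dependent: δ = 0.192 / 0.116 = 1.66, giving about 38%.

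These agree with the simulated 4.8%, 7.5% and 38.5% within Monte Carlo error.

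**Bias or standard error?** At 30% at random the model SE under the SAP rule is 0.119, against 0.129 with multiple imputation (8% lower). The SAP estimator's own sampling spread was 0.117, close to its model SE. The damage is therefore mainly bias.

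**With a true hazard ratio of 1.30 per SD.** The SAP rule gave 1.32, 1.34, 1.38 and 1.41 at 5, 10, 20 and 30% at random, and 1.48 to 1.58 under dependent missingness. Multiple imputation gave 1.30 to 1.32. Coverage of the 95% interval under the SAP rule fell to 0.89 (30% at random) and 0.59 (30% dependent).

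**Sensitivity to the assumptions.** Three other null simulations, all with 800 subjects or a similar number, used different inputs.
- About 145 events, three confounders (OR 2 with the marker, HR 2): false positives with full data versus the SAP rule were 5.5% versus 5.5% at 5% missing, 6.5% versus 6.8% at 10%, and 3.5% versus 9.2% at 20%. The last comparator is itself below nominal by more than the Monte Carlo error of about 1 point.
- About 80 events, five confounders with two incomplete at random, 1,500 replicates: shifts were +0.003, +0.008 and +0.016 at 2, 5 and 10% missing. False positives were 5.1% versus 4.9%, 4.6% versus 4.9%, and 4.9% versus 5.1%.
- About 70 events, three of four confounders incomplete: shifts were about +0.01 at 3%, +0.02 to +0.03 at 10% and +0.04 to +0.05 at 20%. False positives rose by at most about 1 point.

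**The case against.** The best defence is that little will be missing. The covariates are baseline history in inpatients with a confirmed MI. The eCRF checks completeness at entry (SAP 5.1), and missing data are queried to sites (Protocol 10.7). Of the three confounders named from the pilot, age and diabetes are eligibility factors; only prior revascularization is not. This makes low missingness plausible but does not establish it. Two of five factors suffice for entry, so the others need not all be known. The schedule in Protocol 1.3 mandates no imaging for LVEF. A query cannot recover what was never measured.

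A second defence is that SAP 5.2 shows missing counts where applicable, and SAP 5.7.1 also fits FcγRIIa alone. That fit is untouched by covariate imputation and shows how far adjustment moves the estimate. It does not show how much adjustment the fill-in lost.

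Two stronger readings are tempting and should be resisted.

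First, a reader might take the 16 to 39% false-positive rates as the expected error. They require missingness tied to FcγRIIa itself, in four covariates at once. FcγRIIa is assayed at a core laboratory (Protocol 2.3 and 4.1), so sites recording history would not normally know it. Missingness could still follow age or illness severity, but no simulation isolated that case. The assumed confounding was also strong: in the 20% random scenario the unadjusted fit gave a hazard ratio of 1.40 where the truth was 1.00. In the pilot, FcγRIIa was the only covariate associated with MI, stroke and death (Protocol 2.3), though that study was too small to exclude confounding.

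Second, a reader might infer that the fill-ins contaminate the prediction model's error rates, since their evaluation "will be based on a leave-one-out cross-validation approach". The SAP does not say where fill-ins are computed. Dropping one of about 800 subjects barely changes a median or mode, and neither uses the outcome.

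**Conclusion.** The point holds in a limited form. The rule under-adjusts whenever a covariate related to both FcγRIIa and the endpoint is incomplete. The bias is away from the null when the factor raises both, and that sign is an assumption for each covariate.

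Under the assumed inputs, the effect is negligible at about 5% missing or less and small at 10% completely at random. It is potentially material at 20% or more, or when missingness depends on the marker or other risk factors. Even at 20% completely at random the settings disagree, from a rise of about one point or less to a rate of 9.2%.

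The documents do not show that the primary result will be biased to any particular degree. They show a rule that is safe only if very little is missing, with nothing in the plan to test it.

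**What to change.** In SAP 5.9, make multiple imputation by chained equations the primary method for missing covariates in the primary and bleeding Cox models. Use, for example, 20 or more data sets. The imputation model should hold all model covariates, FcγRIIa, and the event indicator and cumulative baseline hazard for the outcome analysed. Combine results with Rubin's rules. Report the missing count for every covariate, not only where applicable. Keep the median/mode rule as a sensitivity analysis, or as the working rule where missingness is trivial (about 1% or less).

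Complete-case analysis is not a good substitute as the primary method. With four covariates each 20% missing at random, only 0.8⁴ = 41% of subjects remain, and the mean SE in the main simulation was 0.198 against 0.126 with multiple imputation.

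The leave-one-out evaluation of the prediction model needs no change on this account, and imputing within each fold is not required.

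The cost is SAP wording, modest extra programming in R (already specified in SAP 5.2) and longer run time. No new data are needed. Fixing the method before the data are seen also avoids a later data-driven choice.

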5.9.1 Missing and Partial Dates

The following rules apply when the date of a primary endpoint is fully or partially missing.

Missing Date: The date will be imputed as the last date of complete follow-up for MI and stroke, and the last known alive date for death.

Missing Year, Month, Day: The imputed value will be the largest value such that the date falls within the subject's known follow-up time. If more than one component of the date is missing, the order of imputation is year, month, day.

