## 1.3 SCHEDULE OF ACTIVITIES

Procedures	Day 1 (prior to or on day of hospital discharge) a	Week 2 to Week 6 after study enrollment	Telephone Study Visit every 6 months (+/- 4 weeks)	Final Telephone Study Visit (+ 2 weeks after at least 80 ischemic events accrued)
Informed Consent	X			
Inclusion/Exclusion Criteria	X			
Clinical Characteristics	X			
Enrollment	X			
Anti-thrombotic Medication Review	X		X	X
Blood Sample to Quantify FcγRIIa b	X	X d		
Assess for Study Endpoints c			X	X
Complete Case Report Forms (CRFs)	X		X	X
	
a: Procedures can be done at any time after confirmation of myocardial infarction index event and prior to hospital discharge. Day 1 is defined as the day the subject is enrolled into the study and must occur prior to or on the day of hospital discharge.
 
b: Approximately 3 ml to 6 ml blood sample. Blood can be taken up to 2 weeks post-study enrollment.
 
c: Endpoints include Ischemic events (MI, stroke, death) and clinically significant bleeding BARC type 2-5.
 
d: For sites participating in the substudy, a 3 ml to 6 ml blood sample will be drawn 2 to 6 weeks after enrollment into the study
			

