## 4 STUDY DESIGN

### 4.1 OVERALL DESIGN

This is a prospective, observational multicenter non-interventional cohort study designed to integrate into the regular standard of care (Figure 5, Schematic Overview). Subjects who are admitted to the hospital with an MI will be screened. Screening will entail review of the medical

record for selected entry criteria. If the subject meets entry criteria, written informed consent will be obtained. Subjects will be enrolled into the study (called Day 1) before discharge from a hospitalization for a confirmed type 1 MI (STEMI or non-STEMI), referred to as the index event. Subjects will not have their care altered by participation in the study; subjects' medical regimens will be determined by their health care provider. Enrollment of subjects who are receiving anticoagulants for atrial fibrillation or venous thromboembolic disease will be limited to approximately 100 subjects.

[figure not shown]
After informed consent is obtained and the subject eligibility is confirmed, each subject will be assigned a unique identifier. Clinical characteristics and biochemical results will be associated with the unique identifier. The association between the subject's identity and the unique identifier will be kept in a secure file. Clinical characteristics will be recorded and blood (approximately 3 ml to 6 ml) will be obtained for analysis of platelet FcγRIIa expression. Blood can be taken up to 2 weeks post-study enrollment. The samples for platelet FcγRIIa expression will be assayed by a core laboratory to ensure standardization.

Subjects will be contacted by telephone every 6 months and asked a standardized set of questions to determine whether they have had a cardiovascular event (MI, stroke), bleeding event or have died. At each study visit, subjects will be queried about their medications with a specific focus on their anti-thrombotic regimen. Changes to their anti-thrombotic regimen will be documented in association with the time when changes were made. All subjects will be contacted at the end of the study for a final telephone visit. Medical records will be reviewed to confirm subject reported endpoints.

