The primary endpoint will be the composite of death, MI, and stroke. MI will be defined in accordance with the 4th universal definition (Thygesen 2018) and stroke consistent with consensus guidelines (Sacco 2013). The incidence of clinically significant bleeding will be determined using the Bleeding Academic Research Consortium (BARC) scale (Mehran 2011) and is defined as BARC type 2-5. Study endpoint events will be confirmed by the review of medical records by the investigator and all relevant medical records will be obtained by the site for submission to the sponsor (as described in Section 10.8). Subjects who experience an endpoint event will continue to be followed throughout the entire study and any subsequent endpoint events will also be confirmed and recorded. See Appendix 1 for study endpoint event definitions.

A total of approximately 800 subjects will be enrolled at approximately 10-20 sites in the US. It is anticipated that it will take about 12 months to enroll the total number of subjects. The study and subject follow-up will continue until 1) at least 80 ischemic events (MI, stroke, and death) have occurred, and 2) the last subject enrolled has completed at least 18 months of follow-up. Based on an annual ischemic event rate of 10%, the overall length of participation in the study is anticipated to be up to 3 years. Results will be monitored during the course of the study.

Figure 5 Schematic Overview of the Study

MI=myocardial infarction; NSTEMI= non-ST-segment elevation MI, STEMI= ST-segment elevation MI

\* Subjects who experience an endpoint event will continue to be followed throughout the entire study and any subsequent events will also be confirmed and recorded.

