5.3 Study Subjects

A clear accounting of the disposition of all subjects who enter the study will be provided, and a summary of the number and percentage of subjects by center will be produced.

A subject is considered to have completed the trial if the subject has adequate follow-up to assess all study outcomes through either the final study telephone visit or the date of death. For subjects who did not complete the trial two different dates are of interest: the last date for which information on nonfatal study outcomes is available and, if later, the date the subject died or was last known to be alive. The

latter can differ from the former when public records are used to determine vital status in a subject who is lost to follow-up.

Completeness of follow-up for the primary endpoint can therefore be assessed in multiple ways, and will be tabulated as follows:

1. Percentage of subjects with complete follow-up for all study outcomes through the final study telephone visit or the date of death
2. Percentage of subjects with complete follow-up for primary study outcomes through the final study visit or the occurrence of a primary study outcome,
3. Percentage of subjects with complete follow-up for vital status
4. Mean percentage of potential follow-up for primary study outcomes as defined in 2 above (defined as 100% for a subject with complete follow-up, or 100 times the number of days of complete follow-up divided by the number of days between the subject's Day 1 visit and the end of study for a subject with incomplete follow-up)
 - a. This percentage of follow-up will be subdivided into percentages of follow-up on DAPT and on monotherapy.
5. Mean percentage of potential follow-up for vital status as defined in 3 above (defined as 100% for a subject with complete follow-up or a subject who died, or 100 times the number of days of vital status follow-up divided by the number of days between the subject's Day 1 visit and the end of study for subjects with incomplete follow-up)

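### SAP 5.9.1 can date an undated MI or stroke many months after the call that reported it, and an undated death as early as possible; contact dates should bound the imputation

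*SAP*

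**What the plan says.** SAP 5.9.1 has two rules for the date of a primary endpoint.

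- Fully missing: "The date will be imputed as the last date of complete follow-up for MI and stroke, and the last known alive date for death".
- Partly missing: "The imputed value will be the largest value such that the date falls within the subject's known follow-up time". Year is filled before month and month before day. There is no separate rule for death.

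For subjects who do not complete the study, SAP 5.3 describes two dates. One is "the last date for which information on nonfatal study outcomes is available". The other, if later, is "the date the subject died or was last known to be alive". Neither is tied to the contact at which an event was reported.

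Protocol 4.1 sets the contact pattern: "Subjects will be contacted by telephone every 6 months". The Schedule of Activities (Protocol 1.3) allows 4 weeks either side of each call. Protocol 4.1 also states: "Subjects who experience an endpoint event will continue to be followed throughout the entire study". Nothing in either document limits an imputed date to the reporting call or to the interval between calls.

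**The concern.** The date of complete follow-up usually falls well after the call that reported the event. An MI or stroke with no date can therefore be entered at a time when the study already knew it had happened. An undated death is handled the opposite way: nobody dies before the day they were last known alive, so that day is the earliest possible date. Two components of one composite endpoint thus err in opposite directions, although the contact records usually give both a lower and an upper bound.

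Four things could be affected:

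- the order of events within a subject, and so which one ends the time to first event;
- the event times in the separate MI, stroke and death models (SAP 5.7.1);
- the DAPT covariate in SAP 5.7.1, which depends on what was taken before the endpoint;
- the person-time in the exposure-adjusted rates used to explore the FcγRIIa threshold.

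**Working it through.** The plan gives no figure for this rule, so there is none to reproduce.

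**Inputs from the documents.** 800 subjects; about 12 months of accrual; at least 18 months of follow-up for the last subject; an annual event rate of 10%; participation of up to 3 years; calls every 6 months, ±4 weeks. Closure at month 30 (12 + 18) gives follow-up of 18 to 30 months.

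**Assumptions, not in the documents.** 60% of first events are MI or stroke and 40% are deaths. Dates are missing completely at random. A binary marker stands in for continuous FcγRIIa.

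**1. Undated MI or stroke.** Error = end of follow-up − true month. Time past the report = end of follow-up − reporting call. For an MI in month 4, reported at the month-6 call:

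| Follow-up (months) | Imputed month | Error (months) | After the report (months) |
|---|---|---|---|
| 18 | 18 | 14 | 12 |
| 24 | 24 | 20 | 18 |
| 30 | 30 | 26 | 24 |
| 36 | 36 | 32 | 30 |

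In simulation (300 data sets per setting, follow-up uniform on 18 to 30 months), undated MI and stroke moved later by about 12.6 months on average. About 89% were dated after the reporting call. In the other 11% or so that call was the last contact, and the imputed date equals it.

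**2. Undated death.** With calls on schedule, the date is at most 6 months too early, or about 8 months at the widest windows (6 months + 4 weeks + 4 weeks). The simulated mean was about 2.8 months early.

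**3. Partial dates.** If only the year is known, the date goes to the end of that year or of follow-up, up to about 12 months late. If the year is missing, it goes to the latest year that fits. Both apply to death as well, so the opposite directions occur only when the whole date is missing.

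**4. Order of events and DAPT.** Take an undated MI in month 4, reported at month 6, then a dated stroke in month 20, with follow-up to month 30. The rule puts the MI at month 30, so the stroke counts as first and the composite time becomes 20 instead of 4. DAPT started between months 4 and 20 would then count as use before the endpoint.

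**5. Primary hazard ratio.** Mean Cox HR under each dating rule:

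| Simulation | Undated | True dates | SAP rule | Midpoint between contacts |
|---|---|---|---|---|
| HR 2, 400 cohorts | 20% | 2.024 | 2.019 | 2.022 |
| HR 1.9, 55% high, 300 data sets | 10% | 1.927 | 1.926 | 1.926 |
| same | 20% | 1.935 | 1.932 | 1.934 |
| same | 50% | 1.913 | 1.897 | 1.907 |

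In the HR 1.9 simulation, the largest shift in log HR in any one data set was 0.024 at 10% undated and 0.085 at 50%. That simulation gives each subject one event, so it does not include the reordering in step 4.

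**6. Pooled rates.**

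- Mean event probability at 0.10 per year over 1.5 to 2.5 years: 1 − (e^−0.15 − e^−0.25)/0.10 = 1 − (0.8607 − 0.7788)/0.10 = 0.181.
- Events: 800 × 0.181 ≈ 145, of which 87 are MI or stroke and 58 are deaths. Person-years: 145/0.10 ≈ 1,450.
- 5% undated: 87 × 0.05 × 12.6/12 − 58 × 0.05 × 2.8/12 = 4.6 − 0.7 = 3.9 person-years, or 0.3%.
- 20% undated: 87 × 0.20 × 12.6/12 − 58 × 0.20 × 2.8/12 = 18.3 − 2.7 = 15.6 person-years, or 1.1%.

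**7. Midpoint between contacts.** The maximum error is half the interval: 3 months on schedule and about 4 at the widest windows. It is larger if calls were missed.

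**The case against.** The strongest reply is that the rule hardly matters. Step 5 shows no meaningful effect on the primary hazard ratio, and step 6 shows about 1% or less on pooled rates. The trigger should also be uncommon. Medical records are reviewed to confirm reported events (Protocol 4.1), source documents go to the sponsor (10.6, 10.8) and missing data are queried (10.7). A confirmed MI or stroke needs troponin or imaging evidence (Appendix 1), which normally carries a date. All of this stands, and it sets the grade of the point.

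A second reply is that complete follow-up might end at the event itself. Protocol 9.4.2 follows subjects to their earliest event, and one completeness measure in SAP 5.3 stops at a primary outcome. This does not rescue the rule: the imputed date would then be defined by the unknown date it is meant to replace.

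A third reply is that contacts do not always bracket an event within 6 months. Calls can be missed, and vital status may come from electronic or public records (Protocol 7.1, SAP 5.3). That is correct. It limits the precision of any contact-based rule, but it does not justify a date later than the report.

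**Conclusion.** The point holds as a minor flaw. As written, SAP 5.9.1 can produce MI and stroke dates that the study's own contact records contradict, by 12 to 24 months in the month-6 example with planned follow-up of 18 to 30 months. It also treats fully undated deaths in the opposite way. The places where this can matter are event order, the component models and the DAPT covariate. How many subjects are affected is unknown, because the documents give no count of undated events.

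A reader might infer more, and the documents do not support it:

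- **That the primary test is biased.** Under random missingness it is essentially unchanged. Missingness related to FcγRIIa was not examined, and nothing in the documents suggests it.
- **That survival curves or an early-versus-late comparison would be distorted**, since the pilot curves separated after 6 months. Neither analysis is planned in SAP 5.7 or Protocol 9.4; the Kaplan-Meier figure in Protocol 2.3 belongs to the pilot.
- **That every incomplete date errs in opposite directions by component.** Only fully missing dates do.

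**What to change.** In SAP 5.9.1, use one rule for MI, stroke and death:

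1. Lower bound: the last contact at which the subject was known to be free of that event (for death, known alive).
2. Upper bound: the contact or record at which the event was first reported.
3. Narrow the interval by any known year or month, and impute its midpoint.
4. Add one sensitivity analysis that uses the earliest and then the latest date in the interval.

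The cost is a few sentences in the SAP before database lock. It needs no new data collection, provided call dates are held with the case report forms completed at each call (Protocol 1.3), which is likely but not stated. There is no loss of events or power.
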